- **Aim 2:** To identify mediators and moderators of CETA's effect on the primary outcome (retention and viral suppression by 12 months). Our primary mediator will be IPV and primary moderator will be partner involvement. *Hypothesis:* Reduction in IPV after CETA will mediate improvement in retention and viral suppression among women who receive CETA; partner involvement in CETA will increase the effect size.
- **Aim 3:** To assess the cost and cost-effectiveness of CETA vs. active control at increasing the proportion of unsuppressed women who have experienced IPV who are retained and virally suppressed by 12 months. *Hypothesis:* CETA will involve additional costs vs. standard of care but with better retention and viral suppression at 12 months, making it cost effective.
- **Aim 4:** To explore the experience of receiving CETA from the perspective of CETA participants post-intervention, including knowledge and skills obtained, acceptability of reporting on and discussing violence, as well as perceptions of the impact of CETA 24 months or more post-intervention. *Hypothesis:* The qualitative exploration will provide an in-depth understanding on the real experiences, perceptions and acceptability of CETA and durability of the intervention.

OVERVIEW OF STUDY DESIGN

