In order to achieve all three aims, we will conduct an individually randomized trial of the effectiveness of CETA for improving viral suppression and retention in HIV care among virally unsuppressed women experiencing IPV. Recruitment will be from an HIV clinic and we will enroll women who: 1) have experienced IPV within the last 12 months; 2) have initiated HIV treatment; and 3) have a last unsuppressed viral load or who have defaulted on treatment or missed or were late for visits in the last year. Women will be encouraged to invite a partner to be part of the CETA intervention. The woman will be the unit of analysis. The primary outcome is a composite measure of retention in care and viral suppression by 12 months. Because it is critical to know if any effects of CETA on retention and suppression are sustained, we will continue to follow women for a total of 24 months, approximately 21 months after CETA is complete, to identify long term effects. We will also assess whether having a partner involved in CETA is a moderator of CETA's effects and examine possible mediators of CETA's impact on HIV outcomes, including IPV, mental health and substance use. Potential mediators and moderators will be measured with a battery of instruments and administered using a tablet-based questionnaire. This study is an effectiveness trial in that recruitment and care will be conducted within care systems already in place.

To achieve the 4th aim, we will conduct 3 focus group discussions (with 6-10 participants per group) and 10 in-depth interviews with study participants (this may include those who have been part of the FGD) post-intervention who completed the intervention in 2023. We will also conduct 5 in-depth interviews with the clinic healthcare providers (adherence counselors) and 5 in-depth interviews with CETA providers. The maximum total sample size for this objective will be 50 participants. All participants will be purposively selected.

STUDY SITES AND POPULATION

a. Study Sites

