Recruitment of participants for the qualitative phase of the study, will be done in the post intervention period. All those participants who were enrolled into the CETA study and randomized to the CETA treatment arm between 1 January and 31 July 2023 will be contacted via SMS using the contact details they provided, and asked if they are interested in participating in a follow-on discussion to the intervention. Those study participants who can be reached and express an interest in participating will then receive a phone call from the study team member who will explain the additional consent process. The full informed consent process will be completed in person before the FGDs and IDIs.

The recruitment process will adopt a purposive sampling method, as we are only selecting participants from the treatment arm who completed the intervention in 2023, making the sampling population much smaller, so this method will allow us, to maximize on the available population size to gain in-depth insights from the participants. For the recruitment of healthcare providers and CETA providers, they will be contacted and informed about this phase of the study and then asked if they will be interested in participating, informed consent will be conducted before the interview.

e. Screening and Screening Consent

Patients who agree to be referred to a member of our study team will receive a brief consent form only for screening to determine eligibility. This conversation will take place in a private location and include only the study staff and the patient. Potential participants will be counseled that they can refuse to participate in the study and still receive HIV care at the treatment site with no risk to the quality of care they receive. The short consent form will explain what questions participants will be asked, including questions related to IPV, as part of the screening process. All those consenting to be screened will be assigned a unique Screening ID (generated *a priori* by a study team member) and administered a screening questionnaire to confirm the inclusion/exclusion criteria. This will include the Severity of Violence Against Women Scale (SVAWS) physical/sexual violence subscale to assess IPV exposure, which previously been used among women who experienced IPV in South Africa. This is a self-administered tablet-based form. Results of the screening will be documented on a tablet-based screening form

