For women who choose T-CETA we will work with them during the initial in person session to determine ways to keep them safe. We will discuss the risks associated with T-CETA to ensure they have a clear understanding of the potential for their conversations to be overheard and the risk for violence should an abusive partner hear the conversation. This session will include planning to ensure they have a safe and private place to be when in T-CETA sessions, having the option for the participant to contact the team using a free “call me” text message to inform the counsellor they are ready and in a safe place if they choose and ways that any communications between the counselor and the participant can be coded to ensure privacy. For example, rather than asking, "are you in a safe and private space for today's session?" the counselor might use an initial coded question tailored to that participant associated with several possible benign responses, determined in advance, to indicate "YES" I am alone, it's ok to continue, or "NO" I can't talk, with an exit strategy planned as well. The safety plan will also include a pre-determined plan to decide what will happen if the counsellor hears voices in the background, or the participant's tone of voice changes, etc. These can include changing the topic of conversation or ending the conversation completely and then later rescheduling the session.

We will end each T-CETA session with a plan for determining the success of the T-CETA approach and any plans to change to in person CETA. This can be done in coded form if the participant wants.

j. Follow-up and Retention

There will be four data collection points: baseline, and 3, 12, and 24 months post baseline. For a purposively selected sample of those participants (n=40) who completed the intervention in 2023 there will also be a qualitative data collection point around 24 months (+/- 3 months) post intervention. Electronic medical records will be obtained to assess our primary outcome. This data collection will be completed in-person. We will assess, violence, mental health and substance use at 3 data collection points: baseline, 3 months post-baseline (the approximate length of CETA treatment and again at 12 months (Figure 2). Because our primary outcomes are retention based (retention and viral suppression) we have no plan to retain patients in the study beyond outreach to complete the CETA intervention. Any effort to do so would undermine the results of the trial.

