Follow-up data for the *primary outcome* for both arms will be passively gathered using routinely collected medical records from the clinics. This is important as any attempts at active follow up would impact our primary outcome, which is viral suppression and retention. As noted, we have successfully used this process at Themba Lethu in the past as data collection is strong and mostly electronic at this site. Themba Lethu has a direct data link with the National Health Laboratory Service which completes all the lab work. Thus, if a viral load is done, no data entry is required for the result to be in the electronic data record at the site. We will not implement any other data collection or follow-up procedures during the study. We will extract the data on all clinic visits and viral loads at 3-, 12- and 24-months post baseline.

c. Secondary outcome data

The tablet-based questionnaire assessments (described above) will be repeated at 3 months post-baseline (end of the CETA intervention) and at 12 months post-baseline for both arms. Although the 3 month time-point could impact the primary retention-based outcome, we feel it is important given the dynamic nature of mental/behavioral problems, and any impact should be equal across arms. With the exception of contacting participants for post-baseline assessments and safety checks, study staff will not

contact participants. Questionnaire data will also provide key patient-level data for evaluating costs and we will also collect resource utilization data (drugs, lab tests, supplies, staff cadre consulted etc.). For patients in the control arm for whom we identify significant mental health issues, we will refer for care.

For the qualitative component, focus group discussions and in-depth interviews will provide an in-depth understanding and insight on perceptions, experiences, feasibility, acceptance and durability of the CETA intervention.

d. Data Sources

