Study subjects will not incur any costs from study participation in the study though they may incur transportation costs for CETA study visits. Participants will not incur costs for text messaging or airtime as the program will pay for all messages that are sent to the participant, for messages that are responses to the safety questions and for talk time for CETA sessions done by telephone/video. Participants will be reimbursed 150 rand per study visit. For CETA visits, because adherence to the protocol and retention in care are our outcomes, payment for study visits would have an influence on the outcome and make it impossible for the intervention to be used in practice. Instead for CETA visits we will be reimbursed 50 rand per visit for the cost of transportation if the sessions are completed by telephone, sufficient talk time will be provided for the T-CETA sessions.

i. k. Qualitative Participants – Costs and Payments

Participants, CETA users and CETA providers will be reimbursed R350 rand per study visit, for an FGD and IDI to reimburse them for their time and travel costs.

DATA SAFETY AND MONITORING PLAN

a. Roles and Responsibilities

The PIs, with the assistance of co-investigators, will assume principal responsibilities for monitoring the consent, data collection, data security and safety of the participating staff from the service institutions. As databases are completed, they will be checked for completeness by a member of the study team to ensure missing or illogical data are corrected when possible. Bi-monthly updates on study enrollment numbers and randomization allocation will be sent by the site study team to the MPIs for monitoring progress. Data completeness and quality will also be reviewed on a monthly basis by Drs. [name] and [name]. Calls with the local study team (at least every two weeks, often weekly) will be conducted by [name] and [name], and the CETA intervention will include weekly supervision by the local PI.

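### The qualitative phase contacts CETA-arm women only and may do so before their passive 24-month records close, which could bias the secondary 24-month comparisons

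*Combined protocol and SAP*

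**What the plan says.** **Who is contacted.** Study Procedures, section d (recruitment for focus groups and interviews), says that women "randomized to the CETA treatment arm between 1 January and 31 July 2023 will be contacted via SMS". Those who can be reached and "express an interest in participating will then receive a phone call from the study team member". Sessions are held in person at the facilities used for the trial (Data Sources, subsection iv), and "CETA users and CETA providers will be reimbursed R350 rand per study visit" (Costs and Payments, qualitative participants). The Sample Size section caps trial women in this phase at 40. No equivalent contact is described for control women.

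**When.** Section d gives no earliest date for the SMS beyond its being after the intervention. Follow-up and Retention (Study Procedures, section j) sets "a qualitative data collection point around 24 months (+/- 3 months) post intervention". Aim 4 in the Objectives instead concerns "perceptions of the impact of CETA 24 months or more post-intervention".

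**The outcomes in play.** The Overview of Study Design says "we will continue to follow women for a total of 24 months, approximately 21 months after CETA is complete, to identify long term effects". Suppression and attrition at 24 months are listed secondary outcomes, taken from routine clinic records up to 24 months post-baseline (Data Sources, subsection i).

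**The plan's stance on contact.** On active retention of women, section j says: "Any effort to do so would undermine the results of the trial". It accepts the 3-month questionnaire because "any impact should be equal across arms". Section j lists qualitative data collection among the permitted contacts. The parallel sentence under Secondary outcome data does not list it.

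**The concern.** The 24-month comparison is meant to show whether any CETA effect lasts. It relies on both arms being left alone, so that attendance and viral load testing reflect the randomised treatment and nothing else. A text, a call and a paid visit to a trial facility, offered to one arm shortly before the record closes, could prompt some women to re-engage with care or have a viral load taken. The plan's defence of the 3-month questionnaire, that both arms are affected alike, cannot apply to a contact that only one arm receives. The exception for qualitative contact does not address this. Costs and Payments itself declines to pay for CETA visits as study visits because payment would influence the outcome.

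If some contacts fall before month 24, part of a CETA advantage at that point could reflect the invitation and not durability. The plan has no analysis that would detect or bound this.

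**Working it through.** **1. The plan's own clock.** The Overview equates 24 months of follow-up with about 21 months after CETA. 24 − 3 = 21, so the figure reproduces with a 3-month CETA course.

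**2. Interview window in months post-baseline.** Opening = CETA end + 21; closing = CETA end + 27. Months = weeks × 7 / 30.4375. Sessions are weekly, typically 6 to 12 (description of CETA); the qualitative phase requires at least 5.

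| CETA length | CETA end (months) | Window opens | Before month 24 | Opens under Aim 4 (CETA end + 24) |
|---|---|---|---|---|
| 5 weeks | 1.15 | 22.15 | 8.0 weeks | 25.15 |
| 6 weeks | 1.38 | 22.38 | 7.0 weeks | 25.38 |
| 12 weeks | 2.76 | 23.76 | 1.0 week | 26.76 |
| 3 months (nominal) | 3.00 | 24.00 | none | 27.00 |

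Interviews can therefore precede month 24 only for women who finish faster than the nominal 3 months. Under Aim 4's wording none do.

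**3. The SMS.** Women randomised 1 January to 31 July 2023 reach month 24 between 1 January and 31 July 2025. The current text records DSMB sign-off in March 2025. The documents give no sending date. Assuming one batch and even accrual over the 212 days, the share texted before month 24 is:

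- 1 April 2025: 122/212 = 58%
- 1 June 2025: 61/212 = 29%
- 1 August 2025: 0%

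If texts instead went out only once each woman's interview window had opened, those still short of month 24 on 1 April would be about 49/212 = 23% (6-week CETA) or 7/212 = 3% (12-week CETA).

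**4. Primary outcome.** Viral loads count up to 18 months. For the last invited woman, 31 July 2023 + 18 months is the end of January 2025, before the March 2025 date in the current text.

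**5. Possible size.** Shift in the risk difference (points) = 100 × n × f × c / 200, where n is the number of CETA women contacted in time, f the share who would otherwise fail, and c the share of those converted by the contact. Assumptions: 200 per arm; f = 0.60, from the 40% control success at 12 months in the Sample Size section; c between 5% and 25%.

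- n = 10, c = 5%: 100 × 10 × 0.60 × 0.05 / 200 = 0.15
- n = 10, c = 25%: 0.75
- n = 40 (all attendees), c = 5%: 0.6
- n = 40, c = 25%: 3.0

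With 40% success and no true effect, a shift of 1 point would raise the two-sided 5% error rate to about 5.5%, and 3 points to about 9.3%.

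**6. An unstated input.** No viral load window is given for the 24-month outcome. If it had the same six-month extension as the 12-month outcome (an assumption), records would close at month 30, and on the nominal clock the whole 24-to-30-month interview window would overlap.

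**The case against.** Much of the case on the other side stands.

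- On the nominal 3-month course, interviews open exactly at month 24. The earlier opening needs unbroken weekly sessions, and the plan calls 6 to 12 sessions typical, not fixed.
- Section j expressly permits qualitative contact, so the phase does not break the no-contact rule as written there. The gap is that the exception ignores the contact being one-armed.
- Only interested responders are phoned and at most 40 women are paid; Data Sources, subsection iv, limits these to Zola CHC. Women who completed at least 5 sessions and reply are plausibly already better retained, leaving fewer failures to convert.
- The invitation concerns a discussion, not HIV care. Attending is not a clinic visit and yields no viral load.

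A reader might infer that the 24-month result is already biased, and by up to several points. For example, take about 64 women texted (200 / 22 × 7, assuming even enrolment from November 2021 to August 2023). Crediting a 10 to 20 point gain to everyone reached before month 24 gives 0.9 points (29% reached, 10-point gain) to 3.7 points (58% reached, 20-point gain). The documents do not support this. The batch dates are assumed, and the accrual dates come from a provider eligibility criterion. The gain is credited even to women who never reply, although the plan treats 20 points as a meaningful effect for CETA as a whole.

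These points limit the size. They do not remove the one-arm contact, the undated SMS, or the conflict between section j and Aim 4.

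**Conclusion.** The concern holds as a possibility the plan leaves open. Qualitative contact goes to CETA women only. The SMS has no lower time limit, and the interview window can open about 1 to 7 weeks before month 24 for women who complete 6 to 12 weekly sessions without interruption. This could bias the secondary 24-month suppression and attrition comparisons, probably towards CETA. The amount is unknown and probably small: about 0.15 to 3 points, given 10 to 40 women contacted in time, 60% who would otherwise fail, and 5% to 25% of those converted. None of these response inputs comes from observed data.

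A stronger reading, that the sustained-effect result is biased or that the trial's main conclusion is at risk, does not follow. Overlap is permitted, not shown, and the primary outcome closes before this phase. Separately, section j and Aim 4 disagree on timing and need to be reconciled whatever the size of the bias.

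**What to change.** 1. In Study Procedures, section d, add that no qualitative SMS, call or visit takes place before the woman's 24-month clinic-record cut-off, and state that cut-off, including the viral load window.
2. In section j, replace the ± 3-month window with one that starts at 24 months post intervention, as in Aim 4. Bring the no-contact sentence under Secondary outcome data into line with section j.
3. Log the date of every qualitative contact.
4. If any woman was contacted before her cut-off, add a 24-month sensitivity analysis that excludes, in both arms, women randomised in the affected calendar period. Randomisation date is fixed before treatment, so the comparison stays randomised.

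**Cost.** Mostly wording and an invitation list ordered by randomisation date. With a cut-off at month 24, the last woman is released on 31 July 2025. Her interview window would open by about the end of October 2025 on a 3-month course (27 months after 31 July 2023), before the January 2026 limit of the no-cost extension. Some interviews move later, and a woman who finished CETA at the end of 2023 would become eligible only at the end of 2025. A cut-off extended to month 30 would push the last release to about the end of January 2026, leaving almost no room.

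The sensitivity analysis loses precision. If the whole January to July 2023 period is affected and enrolment was even over 22 months, it drops 7/22 = 32% of each arm and widens intervals by about 21% (√(22/15) = 1.21).
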